8.2 Estimated Enrollment Period

This study will enroll 360 patients at 9 Regional Clinical Centers (RCCs) and associated satellite centers in the United States and Canada. It is projected that 18 patients per month will be enrolled (2 pts/RCC/month), for a total anticipated enrollment period of approximately 20 months.

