9.1 Randomization

After providing informed consent and signing the ICF, all study subjects will be randomized using procedures determined by the DCC to one of 3 treatment groups. **Patients will be randomized to the nesiritide or dopamine strategy in a 1:1 allocation ratio.** Within each strategy, subjects will be randomized to active drug vs. placebo in a 2:1 allocation ratio. A permuted block randomization method stratified by site will be used to ensure relatively equal distribution of subjects to each arm within each clinical site.

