9.2 Baseline Assessments

At the time of randomization, all study subjects will undergo

- Directed history and physical examination, focused on signs and symptoms of congestion
- Vital signs (including O₂ saturation and weight)
- Concomitant cardiovascular medications
- Serum Cystatin C (core laboratory)
- Serum creatinine, BUN, and electrolytes (local laboratory)
- Patient Global Well being assessment (PGA) by VAS (see Appendix C)
- Dyspnea assessment by VAS (see Appendix C)
- Blood sample for biomarkers core laboratory
- Urine Biomarkers

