13.2 Analysis of Primary Endpoints

The primary analysis will be conducted on an intention-to-treat basis. A general linear model with an indicator for randomization to the nesiritide strategy or dopamine strategy, as well as an indicator for the specific treatments being compared, will be used to examine the effect of each treatment on the primary safety and efficacy outcomes. For the primary comparisons, placebo subjects will be pooled across the nesiritide and dopamine strategies. Comparisons of low-dose dopamine vs. placebo and low-dose nesiritide vs. placebo will each be conducted using a Type I error rate of 0.025.

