13.3 Sample Size Justification

A difference of 0.3 mg/L in serum cystatin C is considered to be clinically meaningful. With a conservative estimate of 102 subjects per treatment group and a standard deviation for the change between randomization and 72 hours of 0.62 mg/L (see Owan et.al. 2008 for an estimate at 48 hours)¹⁸, the study would have 88% power to detect a clinically significant difference between low-dose dopamine vs. placebo (or low-dose nesiritide vs. placebo) at the 0.025 two-sided level. A standard deviation for the change of 0.59 mg/L would provide 91% power and any standard deviation of less than 0.68 mg/L would provide greater than 80% power to detect a clinically meaningful difference. Based on prior Heart Failure Network clinical trials, the amount of missing data is expected to be less than 15% for the change in serum cystatin C from randomization to 72 hours. Therefore a sample size of 120 subjects per treatment group will provide adequate power for the serum cystatin C analyses.

In the clinical trial of Owan et.al.¹⁸ the estimated standard deviation for the change in cumulative fluid balance from randomization to 72 hours was approximately 2900 mL.¹⁸ Based on prior Heart Failure Network clinical trials, the amount of missing data is expected to be less than 10% for the cumulative UV at 72 hours. With a Type I error rate of 0.025 and a sample size of 108 evaluable subjects per treatment arm, the study would have 90% power to detect a treatment difference of > 1400 mL and 80% power to detect a difference of > 1224 mL. These power calculations were based on a 2-sample t-test for the hypothesis of equal means.

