13.5 Exploratory Analyses

Analyses comparing the low-dose dopamine and low-dose nesiritide groups will be considered exploratory as they do not directly address the two primary hypotheses of ROSE. However, if both the low-dose dopamine and low-dose nesiritide treatment are statistically superior to placebo, a secondary analysis will be conducted to compare the two active treatment arms.

Further analyses will be conducted to determine whether the effect of low dose dopamine or low dose nesiritide is modified by each of the following covariates:

- Admission blood pressure
- Age (≤ 70 v. > 70)
- Pre-randomization GFR

Estimation of subgroup effects will be conducted within the linear models framework.

For each of the three treatment groups, the relationship between baseline GFR and 72 hour cumulative UV will be estimated using linear regression models. Additional analyses will compare the placebo subjects randomized to the dopamine strategy vs. the placebo patients randomized to the nesiritide strategy to determine whether the presence of the PICC line alters patient outcomes.

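### The primary model in section 13.2 names only strategy and treatment terms; adding baseline cystatin C, baseline eGFR and the randomisation site would gain precision at no cost in patients

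*Protocol*

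**What the plan says.** Section 13.2 describes the primary model as "A general linear model with an indicator for randomization to the nesiritide strategy or dopamine strategy". A second indicator, for treatment, is the only other term named. The purpose given is that this model "will be used to examine the effect of each treatment on the primary safety and efficacy outcomes". So one description covers both co-primary outcomes: change in serum cystatin C to 72 hours (safety) and cumulative urine volume at 72 hours (efficacy). The section also says that placebo patients are pooled across the two strategies for the primary comparisons.

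Other sections describe information that the model does not use:
- **Site.** Section 9.1: "A permuted block randomization method stratified by site will be used". Section 8.2: "This study will enroll 360 patients at 9 Regional Clinical Centers (RCCs) and associated satellite centers". The number of satellites is not given.
- **Baseline cystatin C.** Section 9.2 lists it among the assessments at randomisation, measured at the core laboratory.
- **Baseline eGFR.** Section 6.1 requires it for eligibility, within 15 to 60 mL/min/1.73m². It meets urine volume only in section 13.5, where, separately by arm, "the relationship between baseline GFR and 72 hour cumulative UV will be estimated using linear regression models". It also appears there as a possible effect modifier.
- **Outpatient loop-diuretic dose.** Section 7.1 needs this dose, in furosemide equivalents, to set the starting diuretic, so it is known before treatment starts.

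The power statements in section 13.3 rest on an unadjusted two-sample t-test "at the 0.025 two-sided level".

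**The concern.** Three features of the stated model look inefficient.

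1. **Cystatin C.** A change score subtracts the baseline with a slope fixed at 1. Estimating that slope by putting baseline in the model cannot raise the large-sample variance and usually lowers it. It also removes the effect of a chance baseline imbalance between arms.
2. **Urine volume.** This outcome has no baseline value to subtract, so the stated model uses no pre-randomisation information about the patient. Any baseline variable that predicts urine volume would reduce the residual variance.
3. **Site.** Blocking within site balances the arms within each site. If outcomes differ between sites and site is left out, that variation stays in the error term although the design has already removed it from the treatment contrast. Standard errors are then larger than they need be.

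At stake is the width of the intervals for two primary outcomes, each tested at 0.025 per drug. Validity is not at stake.

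**Working it through.** **Inputs from section 13.3.** Two-sided alpha 0.025. Cystatin C: difference 0.3 mg/L, SD of change 0.62 mg/L, 102 evaluable per arm (120 × 0.85). Urine volume: SD 2900 mL, 108 evaluable per arm (120 × 0.90), differences 1400 and 1224 mL.

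**Step 1: reproduce the stated power** (two-sample t-test, noncentral t, noncentrality = difference ÷ [SD × √(1/n₁ + 1/n₂)]).
- Cystatin C: 0.3 ÷ (0.62 × √(2/102)) = 0.3 ÷ 0.0868 = 3.456, power 88.3% (stated 88%). SD 0.59 gives 91.4% (stated 91%); SD 0.68 gives 81.3% (stated above 80%).
- Urine volume: standard error 2900 × √(2/108) = 394.6 mL. 1400 mL gives 90.1% (stated 90%); 1224 mL gives 80.0% (stated 80%).

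The stated figures hold, and none relies on adjustment.

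**Step 2: cystatin C with baseline in the model, pooled placebo, 102 v 102.** Let ρ be the correlation between baseline and 72 hours, and assume equal variances σ² at the two times. The change score has variance 2σ²(1 − ρ), and the residual after adjustment has σ²(1 − ρ²). The ratio is (1 + ρ)/2. The SD of change is held at 0.62. The protocol gives no ρ, so a range is shown.

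| Assumed ρ | Variance ratio | Residual SD (mg/L) | Power |
|---|---|---|---|
| unadjusted | 1 | 0.620 | 88.3% |
| 0.6 | 0.80 | 0.555 | 94.5% |
| 0.7 | 0.85 | 0.572 | 93.1% |
| 0.8 | 0.90 | 0.588 | 91.6% |
| 0.9 | 0.95 | 0.604 | 90.0% |
| 0.95 | 0.975 | 0.612 | 89.2% |

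**Step 3: urine volume with baseline predictors, pooled placebo, 108 v 108, at 1224 mL.** The SD becomes 2900 × √(1 − R²). The protocol gives no R².

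| Assumed R² | Residual SD (mL) | Power |
|---|---|---|
| 0 | 2900 | 80.0% |
| 0.05 | 2827 | 82.2% |
| 0.10 | 2751 | 84.3% |
| 0.20 | 2594 | 88.6% |

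**Step 4: site.** No between-site variance is given. If site explained a share s of the variance, the same factor √(1 − s) would apply to the SD: an assumed s of 0.01 gives cystatin C power of 88.7%, and 0.05 gives 90.0%. The cost in degrees of freedom is negligible: with 306 evaluable patients, going from no site terms to 50 sites raises the critical t value from 2.253 to 2.255, about 0.1%.

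**Step 5: the strategy indicator.** Steps 2 and 3 assume a truly pooled placebo group. With strategy and treatment indicators both in the model, each drug is contrasted only with placebo patients of its own strategy. There are 60 of these by allocation, so 51 (cystatin C) or 54 (urine volume) evaluable. For cystatin C the variance factor goes from 1/102 + 1/102 = 0.0196 to 1/102 + 1/51 = 0.0294.

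| Outcome | Unadjusted | Adjusted |
|---|---|---|
| Cystatin C, 102 v 51 | 71.1% | 81.2% (ρ 0.6) to 72.3% (ρ 0.95) |
| Urine volume at 1224 mL, 108 v 54 | 60.7% | 63.2% (R² 0.05) to 71.5% (R² 0.20) |

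Adjustment helps under either reading, but the power levels depend on which model is fitted.

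**The case against.** **The covariate list may be left to the SAP.** Section 13.2 does not say that the model is unadjusted or that no other terms are allowed, and the SAP is not at hand. This has some force. But 13.2 does not defer the model: it names the terms for both primary outcomes, so a SAP that added covariates would depart from the protocol's description. Proposing an addition to a stated method is fair; calling it an error would not be.

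**The plan is valid and coherent without adjustment.** This stands in full. Under randomisation the change-score comparison is unbiased, and the sample size was calculated for an unadjusted test and reproduces.

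**The size of the gain rests on assumed values.** This also stands. The correlation, R², between-site variance and equality of variances are not in the protocol. At a correlation of 0.95 the cystatin C gain is under one percentage point.

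A reader might infer more than the protocol supports on three points:
- *That the confidence intervals are wrong because site is omitted.* They are conservative only to the extent that outcomes differ by site, which the protocol does not quantify.
- *That regression to the mean biases the cystatin C comparison.* It acts equally on randomised arms in expectation; only chance baseline imbalance remains.
- *That the protocol itself expects urine volume to depend on GFR.* Section 13.5 plans to estimate that relation and does not assert it. Nor does scaling the diuretic to the outpatient dose say how much urine-volume variance that dose explains.

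**Conclusion.** The point holds as a free improvement to a stated method. It is not an error in the analysis or the sample size. The primary model leaves out baseline cystatin C, baseline eGFR and the randomisation stratum, all available before treatment starts, and so gives up some precision on both co-primary outcomes.

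For the pooled comparison the gain is about 1 to 6 percentage points of power for cystatin C (assumed correlation 0.95 down to 0.6) and about 2 to 9 points for urine volume at 1224 mL (assumed R² 0.05 to 0.20). These ranges are illustrations. The direction of the gain is firm in large samples, but its size is unknown. With the strategy indicator kept, the gains start from about 71% and 61%, so adjustment alone would not reliably restore the power stated in section 13.3. How the strategy indicator fits with placebo pooling is a separate matter that 13.2 also needs to settle.

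**What to change.** In section 13.2:
- add baseline cystatin C as a covariate in the cystatin C model;
- add baseline eGFR, and optionally outpatient furosemide-equivalent dose, to the urine-volume model;
- add randomisation site to both models, with a prespecified rule for pooling very small sites (for example, satellites under their regional center). Pooled sites only approximate the randomisation stratum, so the rule should be fixed before unblinding;
- keep the unadjusted estimates as supportive, since section 13.3 is powered on them.

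The cost is a few lines of text. The baseline values and site are already available, no extra patients are needed, and the degrees of freedom used are negligible. Fixing the covariates in advance also rules out choosing them after the data are seen. Section 13.3 can stay as it is with respect to adjustment.

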13. STATISTICAL CONSIDERATIONS

13.1 Overview

Summaries of continuous variables will be displayed using the mean, standard deviation, median, and 25th - 75th percentiles. For nominal variables, the number and frequency of subjects in each category will be presented. Statistical tests with p-values < 0.05 will be considered statistically significant, unless otherwise stated. Analyses will be performed using SAS software (SAS Institute, Inc, Cary, NC).

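### Testing each drug at a fixed 0.025 is valid but less efficient than Holm's step-down, which adds power when both drugs work and keeps the same 0.05 bound

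*Protocol*

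**What the plan says.** Protocol section 13.2 fixes the rule for the primary analysis: the two drug-versus-placebo tests "will each be conducted using a Type I error rate of 0.025". Placebo patients from the two strategies are pooled for both comparisons. Section 13.3 powers each comparison "at the 0.025 two-sided level", and section 13.1 sets the default: "Statistical tests with p-values < 0.05 will be considered statistically significant, unless otherwise stated". No step-down or other re-use of the error rate is described.

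Two other places bear on the point. Section 2.1 states two primary hypotheses, one per drug. Section 13.5 provides a secondary comparison of the two active arms "if both the low-dose dopamine and low-dose nesiritide treatment are statistically superior to placebo".

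**The concern.** Two tests at 0.025 add to 0.05, so 13.2 reads as a plain Bonferroni split across the drugs. Bonferroni keeps the second drug at 0.025 even after the first has been shown to work, when only one null hypothesis can still be true and 0.05 is available for it. Holm's procedure uses that 0.05.

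At stake is power for the second drug. The loss is largest in the chance of showing that both drugs work. That is the outcome on which 13.5 makes its secondary dopamine-versus-nesiritide analysis depend.

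The protocol itself fixes this rule. An analysis plan that adopted Holm would depart from 13.2, so the sentence should be changed there.

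**Working it through.** **Inputs (section 13.3).** Cystatin C: difference 0.3 mg/L, SD of the 72-hour change 0.62 mg/L, 102 evaluable per arm. Urine volume: SD 2900 mL, 108 evaluable per arm, differences of 1400 and 1224 mL. Each test is at two-sided 0.025. Arms are equal and placebo is shared (sections 5 and 13.2).

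**Step 1. Reproduce the stated powers.** For a two-sample t-test, SE = SD × √(2/n) and the noncentrality is difference/SE.

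- Cystatin C: SE = 0.62 × √(2/102) = 0.0868; 0.3/0.0868 = 3.456; critical value 2.258 on 202 df; power 88.3%. The plan says "the study would have 88% power to detect a clinically significant difference between low-dose dopamine vs. placebo".
- Urine volume: SE = 2900 × √(2/108) = 394.6. For 1400 mL, 1400/394.6 = 3.548, power 90.1% (stated 90%). For 1224 mL, 1224/394.6 = 3.102, power 80.0% (stated 80%).

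The stated figures hold.

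**Step 2. Why Holm keeps the bound.** Holm tests the smaller p-value at 0.025 and, only if it is significant, the larger at 0.05.

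- Both drugs null: a false rejection needs at least one p ≤ 0.025, with probability at most 2 × 0.025 = 0.05.
- One drug null: it can be rejected only if its own p ≤ 0.05, again at most 0.05.

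Neither argument uses the correlation between the tests, so the shared placebo group raises no validity issue. Any p ≤ 0.025 is rejected under Holm too, so Holm never rejects less.

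**Step 3. Size of the gain.** The powers come from simulating three equal arms with a shared control, pooled variance on 3n − 3 df, and two-sided critical values at 0.025 and 0.05 (2.253 and 1.968 for n = 102). The two test statistics have correlation (σ²/n)/(2σ²/n) = 0.5. Separate runs agree to about 0.1 point. The per-drug figure under the fixed rule is slightly above Step 1 because the variance is pooled over three arms.

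| Both drugs at the planned effect | Fixed 0.025 | Holm |
|---|---|---|
| Cystatin C, per drug | 88.5% | 91.9% |
| Cystatin C, both drugs | 81.0% | 87.7% |
| Cystatin C, at least one | 96.0% | 96.0% |
| Urine volume 1224 mL, per drug | 80.2% | 84.7% |
| Urine volume 1224 mL, both drugs | 69.0% | 78.1% |

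The chance of at least one success is the same because the first step is the same. With equal effects, the per-drug gain must then be half the gain for both: (87.7 − 81.0)/2 = 3.35 points for cystatin C and (78.1 − 69.0)/2 = 4.55 for urine volume, as the table shows within rounding.

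**Step 4. Where the gain disappears, and its cost in error.**

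| Configuration | Fixed 0.025 | Holm |
|---|---|---|
| Only one drug works: its power, cystatin C | 88.5% | 88.7% |
| One drug null, other at 0.3 mg/L: null drug declared effective | 2.5% | about 4.5% |
| One drug null, other at 1224 mL: null drug declared effective | 2.5% | about 4.3% |
| Both drugs null: at least one declared effective | 4.6% | 4.6% |

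**The case against.** The strongest reply is that nothing in the protocol is wrong. Testing each drug at 0.025 is valid and pre-specified, 13.3 is powered on exactly that rule, and its figures reproduce. The fixed rule also judges each drug on its own data and matches simple 97.5% intervals. Under Holm, a second drug with p = 0.04 could be declared effective only because the first succeeded, although its 97.5% interval includes zero. All of this stands, and it limits the point to one of efficiency.

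A reader might infer that Holm is free, or that the error is the same in every configuration. Neither is supported. The 0.05 bound is the same, and so is the error when both drugs are null. When only one is null, Holm uses error that the fixed rule leaves unspent.

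A reader might also infer a general gain in power. The gain needs both drugs to be effective, and section 2.1 states two separate hypotheses, so success with both drugs is not itself a primary objective. Nor does 13.5 bar the comparison of active arms if one drug misses: it calls such comparisons exploratory in any case, and only the secondary analysis depends on both succeeding.

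Finally, the powers above use the simple pooled-placebo comparison, as 13.3 does, whereas the model in 13.2 also contains a strategy indicator. Fitted additively, each drug would be compared with its own strategy's placebo only. At 102 per arm the variance factor would be 1/102 + 1/51 = 0.0294 instead of 2/102 = 0.0196, and cystatin C power at 0.025 would be about 72%. That changes the absolute powers. It does not change the ordering, since Holm would still never do worse.

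**Conclusion.** The point holds as a cheap improvement, not as an error. At the plan's own inputs, with both drugs effective, the fixed split gives up 3.4 points of power per drug and 6.7 points for both on cystatin C, and 4.5 and 9.1 points on urine volume at 1224 mL. It gives up nothing in the chance that at least one drug succeeds, and next to nothing if only one drug works.

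This rests on three assumptions. First, the two 0.025 levels are meant to hold 0.05 across the two drugs; the protocol does not name a familywise level, but the sum matches the default in 13.1. Second, the comparison is the plain pooled-placebo one of 13.3. Third, the result applies within one endpoint: how the two co-primary endpoints in 11.1 combine is a separate matter that Holm across drugs does not settle.

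**What to change.** In section 13.2, replace the fixed level with a step-down rule. Within each primary endpoint, test the smaller of the two drug-versus-placebo p-values at two-sided 0.025 and, only if it is significant, test the other at two-sided 0.05. Make the change before unblinding.

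Leave section 13.3 as it is, since its per-drug powers remain lower bounds for the same comparison under Holm. Sample size, conduct and data collection do not change.

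The change has two costs. The 97.5% intervals can still be reported, but they may not match a rejection made at the second step, and the text should say so. A single null drug would also carry a false-positive rate of about 4.5% or 4.3% in place of 2.5%, still below 0.05.

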13.3 Sample Size Justification

A difference of 0.3 mg/L in serum cystatin C is considered to be clinically meaningful. With a conservative estimate of 102 subjects per treatment group and a standard deviation for the change between randomization and 72 hours of 0.62 mg/L (see Owan et.al. 2008 for an estimate at 48 hours)¹⁸, the study would have 88% power to detect a clinically significant difference between low-dose dopamine vs. placebo (or low-dose nesiritide vs. placebo) at the 0.025 two-sided level. A standard deviation for the change of 0.59 mg/L would provide 91% power and any standard deviation of less than 0.68 mg/L would provide greater than 80% power to detect a clinically meaningful difference. Based on prior Heart Failure Network clinical trials, the amount of missing data is expected to be less than 15% for the change in serum cystatin C from randomization to 72 hours. Therefore a sample size of 120 subjects per treatment group will provide adequate power for the serum cystatin C analyses.

In the clinical trial of Owan et.al.¹⁸ the estimated standard deviation for the change in cumulative fluid balance from randomization to 72 hours was approximately 2900 mL.¹⁸ Based on prior Heart Failure Network clinical trials, the amount of missing data is expected to be less than 10% for the cumulative UV at 72 hours. With a Type I error rate of 0.025 and a sample size of 108 evaluable subjects per treatment arm, the study would have 90% power to detect a treatment difference of > 1400 mL and 80% power to detect a difference of > 1224 mL. These power calculations were based on a 2-sample t-test for the hypothesis of equal means.

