11.3 Tertiary Endpoints

- Change in serum cystatin C from randomization to 24 and 48 hr
- Cumulative UV at 24 and 48 hr
- Cumulative urinary sodium excretion (UNaV) at 24 and 48 hr
- Patient global well being assessment by VAS AUC over 24 and 48 hr
- Dyspnea assessment by VAS AUC over 24 and 48 hr
- Change in serum creatinine from randomization to 24 and 48 hr
- Changes from randomization in the bivariate vector of serum cystatin C and

cumulative UV at 24 and 72 hr

For each intervention group and placebo, the change in serum cystatin C at 24 and 72 hours and UV at 24 and 72 hours for each patient will be plotted on a two dimensional coordinate grid along with estimates of the mean effect and a 95% confidence ellipse (separate plots will be produced for the 24-hour data and the 72-hour data). This graphical presentation will allow visual and statistical assessment of the "trade off" between change in serum cystatin C and UV. Comparisons will be constructed for dopamine vs. placebo and nesiritide vs. placebo to visualize the differences between treatment strategies.

• Changes from randomization in the bivariate vector of creatinine and weight at 24

and 72 hr

For each ingtervention group and placebo, weight loss at 24 and 72 hours and change in creatinine at 24 and 72 hours for each patient will be plotted on a two dimensional coordinate grid along with estimates of the mean effect and a 95% confidence ellipse. This graphical presentation will allow visual and statistical assessment of the "trade off" between change in weight and change in renal function. Comparisons between dopamine vs. placebo and nesiritide vs. placebo will be constructed as described above to visualize the differences between treatment strategies.

- Time from randomization to discharge from index hospitalization
- Total days alive and free from heart failure hospitalization during the 60 days following randomization
- Changes in circulating biomarkers from randomization to 72 hours
- Changes in Urine biomarkers from randomization to 72 hours, day 7, or discharge if earlier

• Mortality during the six months following enrollment

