13.4 Analysis of Secondary and Tertiary Endpoints

General linear models and nonparametric approaches will be used to analyze the continuous outcomes. For binary outcomes, logistic regression analysis will be used to compare each treatment vs. placebo and estimate the odds ratio and 95% confidence interval for low-dose dopamine vs. placebo and low-dose nesiritide vs. placebo comparisons. Time-to-event comparisons will be conducted using Kaplan-Meier curves and log-rank tests. For analyses of patient global well being VAS and dyspnea VAS, the value of zero will be imputed for all measurements missing due to death. Sensitivity analyses, including the worst-rank score analysis ⁽²¹⁾ will be employed to assess the influence of informatively missing values on the results. In particular the worst-rank score analysis will account for missing data due to deaths.

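### The primary cystatin C model uses only the 72-hour change, so patients without that value drop out although their 24- and 48-hour values are scheduled, and the worst-rank analysis is not extended to the primary endpoints

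*Protocol*

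**What the plan says.** - **Outcome.** Section 11.1 makes the change in serum cystatin C from randomization to 72 hours the primary safety endpoint. That is one number per patient.
- **Model.** Section 13.2 states "The primary analysis will be conducted on an intention-to-treat basis" and names "A general linear model with an indicator for randomization to the nesiritide strategy or dopamine strategy", plus an indicator for the treatments compared. It mentions no baseline covariate, repeated measures or imputation. The two comparisons with pooled placebo "will each be conducted using a Type I error rate of 0.025".
- **Sizing.** In section 13.3, "A difference of 0.3 mg/L in serum cystatin C is considered to be clinically meaningful". Power is given for 102 subjects per group, SD 0.62 mg/L, "at the 0.025 two-sided level", and 120 per group are recruited because "the amount of missing data is expected to be less than 15% for the change in serum cystatin C from randomization to 72 hours".
- **Earlier values.** Sections 9.2 and 10.1 schedule core-laboratory cystatin C at baseline and at 24, 48 and 72 hours for all subjects. Section 10.2 adds day 7, or discharge if earlier. The 24- and 48-hour values appear as an endpoint only in section 11.3: "Change in serum cystatin C from randomization to 24 and 48 hr".
- **Missing data.** The only provisions are in section 13.4, on secondary and tertiary endpoints: zero for VAS scores missing through death, and sensitivity analyses in which "the worst-rank score analysis will account for missing data due to deaths".

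**The concern.** A linear model on a single change score can use only patients who have that score, unless missing scores are filled in. The protocol allows for up to 15% without one, about one patient in seven at that limit, and does not use the values those patients may already have at 24 and 48 hours.

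The reasons for a missing 72-hour value need not be unrelated to the kidney. Section 12.4.1 lists acute renal failure and worsening heart failure as anticipated events, and section 11.2 counts rescue therapy and death within 72 hours as outcomes. Cystatin C is the safety co-primary endpoint. If patients with the worst renal course lack the 72-hour value more often on active drug, the contrast among observed patients understates harm.

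The protocol recognises informative missingness as a threat, but places the analysis for it under the secondary and tertiary endpoints and not with the two primary endpoints.

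**Working it through.** **1. Reproducing the plan's figures.** Inputs from section 13.3: difference 0.3 mg/L, two-sided alpha 0.025, two-sample t-test.

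- Evaluable patients: 120 × (1 − 0.15) = 102 per group, as stated.
- Standard error: 0.62 × √(2/102) = 0.0868 mg/L.
- Power from the noncentral t distribution, n = 102 per group:

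| SD (mg/L) | Computed | Stated |
|---|---|---|
| 0.62 | 88.3% | 88% |
| 0.59 | 91.4% | 91% |
| 0.68 | 81.3% | above 80% |

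All three reproduce, so the sizing is sound.

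**2. Bias in the between-arm difference.** In each arm, let m be the share missing and k the gap in mean 72-hour change between missing and observed patients. The observed mean misses the full-arm mean by m × k. The bias in the difference is therefore m₁k₁ − m₂k₂, which is zero if both quantities are the same in both arms. The documents give no missingness by arm and no gap, so every value of k, and every split of m between arms, is an assumption. No arm is set above 15%.

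Type I error uses the normal approximation with critical value c = 2.241 and SE 0.0868: 1 − Φ(c − b/SE) + Φ(−c − b/SE), where b is the bias.

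| Assumed pattern | Bias (mg/L) | Share of 0.3 | Type I error (nominal 0.025) |
|---|---|---|---|
| 5% vs 15% missing, gap 0.5 in both arms | 0.10 × 0.5 = 0.050 | 17% | 0.050 |
| 5% vs 15% missing, gap 0.62 in both arms | 0.10 × 0.62 = 0.062 | 21% | 0.065 |
| 15% in both arms, gaps differ by 0.31 | 0.15 × 0.31 = 0.047 | 15.5% | 0.047 |
| 15% in both arms, gaps differ by 0.62 | 0.15 × 0.62 = 0.093 | 31% | 0.121 |
| Same rate and same gap in both arms | 0 | 0% | 0.025 |

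For the first row, b/SE = 0.050/0.0868 = 0.576. The upper tail is 1 − Φ(1.665) = 0.048 and the lower tail Φ(−2.817) = 0.002, together 0.050.

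**3. Efficiency from using the earlier values.** Let ρ be the correlation between the 48- and 72-hour changes, and f the share of the 18 patients per group missing at 72 hours who have an earlier value. Both are assumed. A likelihood-based estimate of the 72-hour mean has variance SD² × [(1 − ρ²)/102 + ρ²/(102 + 18f)], and the effective n is SD² divided by that variance.

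| ρ | Effective n (f = 0.5 to 1) | Power |
|---|---|---|
| 0.3 | 102.7-103.4 | 88.6-88.8% |
| 0.5 | 104.1-106.0 | 89.0-89.6% |
| 0.7 | 106.2-110.1 | 89.7-90.8% |
| 0.9 | 109.2-116.1 | 90.5-92.3% |

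With all 120 observed, power would be 93.1%. The gain over 88.3% is about 0.3 to 4 percentage points, so the case for change rests on bias.

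**The case against.** The strongest reply is that handling of missing data is normally left to the statistical analysis plan, which is not shown, and that the protocol nowhere restricts the analysis to patients with a 72-hour value. The second part is true: dropping such patients follows from the model and outcome as written and is not a stated rule. But section 13.2 does not defer the model. It fixes one that cannot use the earlier values, and section 13.4 does address informative missingness, under other endpoints.

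A reader might also infer two stronger points, and the documents support neither.

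- **That the trial is wrongly sized on completers.** Sizing on evaluable patients and inflating for missing data is correct, and the stated power reproduces.
- **That the intention-to-treat label is contradicted.** Section 7.4 uses the term for patients who stop study drug or need rescue; they stay in their randomized group. Expecting some missing outcomes does not conflict with that.

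Other objections stand in part.

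- Bias needs a difference between arms in missingness rate or gap, and nothing in the documents shows one.
- Early discharge should be limited, because section 6.1 requires an anticipated stay of at least 72 hours. Section 10.2 also schedules a sample at an earlier discharge.
- Missing urine volume is put below 10% against below 15% for cystatin C, so some of the cystatin C loss may come from sample problems unrelated to renal course.
- The worst-rank sentence in section 13.4 names no endpoint and does not forbid use for the primary endpoints. Its heading, however, covers only secondary and tertiary endpoints.
- A mixed model relies on missing at random and does not settle deaths before 72 hours. That is why the worst-rank extension is needed as well.

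**Conclusion.** The point holds as an improvement to the analysis that should be made. As written, the primary cystatin C model leaves out patients without a 72-hour value, expected to be fewer than 15%, although their earlier values are scheduled. The one analysis aimed at informative missingness is not extended to the primary endpoints.

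Under the assumed patterns with arm differences, bias is about 0.05 to 0.09 mg/L, or 15% to 31% of the 0.3 mg/L target. Type I error is then about 0.05 to 0.12 against 0.025. If missingness behaves alike in both arms, the bias is nil. These figures show what is possible; the documents do not establish that it will happen. The power gain is small under any assumption examined.

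**What to change.** - **Section 13.2.** Specify a likelihood-based repeated-measures model for cystatin C at 24, 48 and 72 hours, with baseline cystatin C as covariate, the strategy and treatment terms already named, and treatment by time. The test is the 72-hour contrast of each drug with pooled placebo, at the existing 0.025 level.
- **Section 13.4.** Extend the worst-rank sensitivity analysis to both primary endpoints, so that deaths before 72 hours and other informative missingness are addressed there too.
- **Optional.** For urine volume, a missing 24-hour segment could be multiply imputed from the observed segments. Expected missingness is lower there and no problem has been quantified.

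The cost is wording in two sections and slightly more programming, with no new visits, samples or patients. The sample size stays as it is. The statistical price is a missing-at-random assumption in the main model, which should be stated. The model adds nothing for patients with no post-baseline value.
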